3.0 SCREENING AND STUDY ENROLLMENT PROCEDURES

Patient enrollment for this study will be facilitated using the Oncology Patient Enrollment Network (OPEN), a web-based registration system available on a 24/7 basis. It is integrated with the NCI Cancer Trials Support Unit (CTSU) Enterprise System for regulatory and roster data and, upon enrollment, initializes the patient position in the RAVE database.

Access requirements for OPEN:

Investigators and site staff will need to be registered with CTEP and have a valid and active Cancer Therapy Evaluation Program-Identity and Access Management (CTEP-IAM) account (check at <<https://ctepcore.nci.nih.gov/iam/>>). This is the same account (user id and password) used for credentialing in the CTSU members' web site. To perform registrations in OPEN, the site user must have been assigned the 'Registrar' role on the relevant Group or CTSU roster. OPEN can be accessed at <https://open.ctsu.org> or from the OPEN tab on the CTSU members' side of the website at <https://open.ctsu.org>. Registrars must hold a minimum of an AP registration type.

All site staff will use OPEN to enroll patients to this study. It is integrated with the CTSU Enterprise System for regulatory and roster data and, upon enrollment, initializes the patient position in the Rave database. OPEN can be accessed at <https://open.ctsu.org> or from the OPEN tab on the CTSU members' side of the website at <https://www.ctsu.org>. To assign an IVR or NPIVR as the treating, crediting, consenting, drug shipment (IVR only), or investigator receiving a transfer in OPEN, the IVR or NPIVR must list on their Form FDA 1572 in RCR the IRB number used on the site's IRB approval. Please see [Appendix IX](#) for detailed CTEP and CTSU Registration Procedures including: registration in Registration and Credential Repository (RCR), requirements for site registration, submission of regulatory documents and how to check your site's registration status.

3.1 Genetic Screening Procedures for Eligibility

Patient enrollment onto the APEC1621SC screening protocol is required. Tumor and blood samples will be obtained and the results of the evaluation of the tumor specimens will determine if the patient's tumor has an actionable Mutation of Interest (aMOI) for which a MATCH treatment subprotocol is available.

The treatment assignment to MATCH to a subprotocol (if a relevant aMOI is detected) will be communicated to the enrolling institution via the COG or MATCHBox treatment assignment mechanism at the time the results of MATCH are returned, upon which a reservation to APEC1621J will be secured by COG. Reservations should be withdrawn by the institution if at any point the patient indicates they do NOT intend to consent to participation or the site investigator indicates the patient will never be eligible for APEC1621J.

3.2 IRB Approval

In order to participate in Pediatric MATCH, an institution must participate in the NCI Pediatric CIRB. NCI Pediatric CIRB approval of this study must be obtained by a site prior to enrolling patients

Submitting Regulatory Documents: Submit required forms and documents to the CTSU Regulatory Office, where they will be entered and tracked in the CTSU RSS.

Online: <http://www.ctsu.org> (members' section) → Regulatory Submission Portal
Regulatory Help Desk: [contact]

Sites participating on the NCI CIRB initiative and accepting CIRB approval for the study

are not required to submit separate IRB approval documentation to the CTSU Regulatory Office for initial, continuing, or amendment review. However, sites must submit a Study Specific Worksheet for Local Context (SSW) to the CIRB (via IRBManager) to indicate their intention to open the study locally. The CIRB's approval of the SSW is then communicated to the CTSU Regulatory Office for compliance in the RSS. The Signatory Institution must inform the CTSU which CIRB-approved institutions aligned with the Signatory Institution are participating in the study so that the study approval can be applied to those institutions. Other site registration requirements (e.g., laboratory certifications, protocol-specific training certifications, or modality credentialing) must be submitted to the CTSU Regulatory Office or compliance communicated per protocol instructions.

3.3 Informed Consent/Accent

The investigational nature and objectives of the trial, the procedures and treatments involved and their attendant risks and discomforts, and potential alternative therapies will be carefully explained to the patient or the patient's parents or guardian if the patient is a child, and a signed informed consent and assent will be obtained according to institutional guidelines.

3.4 Screening Procedures

Diagnostic or laboratory studies performed exclusively to determine eligibility for this trial must only be done after obtaining written informed consent. This can be accomplished through the study-specific protocol. Documentation of the informed consent for screening will be maintained in the patient's research chart. Studies or procedures that were performed for clinical indications (not exclusively to determine eligibility) may be used for baseline values even if the studies were done before informed consent was obtained.

3.5 Eligibility Checklist

Before the patient can be enrolled, the responsible institutional investigator must sign and date the completed eligibility checklist. A signed copy of the checklist will be uploaded into RAVE immediately following enrollment.

3.6 Study Enrollment

Following a MATCH treatment assignment to a protocol, patients may be enrolled on the study once all eligibility requirements for the study have been met. Before enrolling a patient on study, the Study Chair or Vice Chair should be notified. Patients who give informed consent for the protocol in order to undergo screening for eligibility are not considered enrolled and should not be enrolled until the screening is completed and they are determined to meet all eligibility criteria. Study enrollment is accomplished by going to the CTSU OPEN (Oncology Patient Enrollment Network) <https://open.ctsu.org/open/>. For questions, please contact the COG Study Research Coordinator, or the CTSU OPEN helpdesk at <https://www.ctsu.org/CTSUCContact.aspx>. Patients must be enrolled before treatment begins. **Patients must not receive any protocol therapy prior to enrollment.**

Patients must be enrolled within 12 weeks (84 days) of treatment assignment. Protocol therapy must start no later than 7 calendar days after the date of enrollment. Patients enrolling onto APEC1621J will have a COG ID obtained through their prior enrollment onto the screening protocol or from a prior COG study.

Note: No starter supplies will be provided. Drug orders of BVD-523FB (ulixertinib) should be placed with CTEP after enrollment and treatment assignment to

APEC1621J with consideration for timing of processing and shipping to ensure receipt of drug supply prior to start of protocol therapy**3.7 Institutional Pathology Report**

The institutional pathology report from the tumor specimen submitted for sequencing will have been uploaded into RAVE immediately following enrollment on the APEC1621 master screening protocol.

3.8 Dose Assignment

The dose level will be assigned via OPEN at the time of study enrollment.

4.0 PATIENT ELIGIBILITY

All clinical and laboratory studies to determine eligibility must be performed within 7 days prior to enrollment unless otherwise indicated. Laboratory values used to assess eligibility must be no older than seven (7) days at the start of therapy. Laboratory tests need **not** be repeated if therapy starts **within** seven (7) days of obtaining labs to assess eligibility. If a post-enrollment lab value is outside the limits of eligibility, or laboratory values are older than 7 days, then the following laboratory evaluations must be re-checked within 48 hours prior to initiating therapy: CBC with differential, bilirubin, ALT (SGPT) and serum creatinine. If the recheck is outside the limits of eligibility, the patient may not receive protocol therapy and will be considered off protocol therapy. Imaging studies, bone marrow biopsy and/or aspirate (when applicable) must be obtained within 14 days prior to start of protocol therapy (repeat the tumor imaging if necessary).

Clarification in timing when counting days: As an example, please note that if the patient's last day of prior therapy is September 1st, and the protocol requires waiting at least 7 days for that type of prior therapy, then that patient cannot be enrolled until September 8th.

Important note: The eligibility criteria listed below are interpreted literally and cannot be waived. All clinical and laboratory data required for determining eligibility of a patient enrolled on this trial must be available in the patient's medical or research record which will serve as the source document for verification at the time of audit.

4.1 Inclusion Criteria

- 4.1.1 **APEC1621SC:** Patient must have enrolled onto APEC1621SC and must have been given a treatment assignment to MATCH to APEC1621J based on the presence of an actionable mutation as outlined in [Appendix VIII](#).
- 4.1.2 **Age:** Patients must be \geq than 12 months and \leq 21 years of age at the time of study enrollment.
- 4.1.3 **BSA:** Patients must have a body surface area $\geq 0.54 \text{ m}^2$ at the time of study enrollment.
- 4.1.4 **Disease Status:** Patients must have radiographically **measurable** disease (See [Section 12](#)) at the time of study enrollment. Patients with neuroblastoma who do not have measurable disease but have MIBG+ evaluable disease are eligible. Measurable disease in patients with CNS involvement is defined as tumor that is measurable in two perpendicular diameters on MRI and visible on more than one slice.

Note: The following do not qualify as measurable disease:

- malignant fluid collections (e.g., ascites, pleural effusions)
- bone marrow infiltration except that detected by MIBG scan for neuroblastoma
- lesions only detected by nuclear medicine studies (e.g., bone, gallium or PET scans) except as noted for neuroblastoma
- elevated tumor markers in plasma or CSF
- previously radiated lesions that have not demonstrated clear progression post radiation
- leptomeningeal lesions that do not meet the measurement requirements for RECIST 1.1.

4.1.5 **Performance Level:** Karnofsky $\geq 50\%$ for patients > 16 years of age and Lansky ≥ 50 for patients ≤ 16 years of age (See [Appendix I](#)). Note: Neurologic deficits in patients with CNS tumors must have been relatively stable for at least 7 days prior to study enrollment. Patients who are unable to walk because of paralysis, but who are up in a wheelchair, will be considered ambulatory for the purpose of assessing the performance score.

4.1.6 **Prior Therapy**

4.1.6.1 Patients must have fully recovered from the acute toxic effects of all prior anti-cancer therapy and must meet the following minimum duration from prior anti-cancer directed therapy prior to enrollment. If after the required timeframe, the numerical eligibility criteria are met, e.g. blood count criteria, the patient is considered to have recovered adequately.

- a. Cytotoxic chemotherapy or other anti-cancer agents known to be myelosuppressive. See <https://www.cogmembers.org/site/disc/devtherapeutics/default.aspx> for commercial and Phase 1 investigational agent classifications. For agents not listed, the duration of this interval must be discussed with the study chair and the study-assigned Research Coordinator prior to enrollment.
 - i. ≥ 21 days after the last dose of cytotoxic or myelosuppressive chemotherapy (42 days if prior nitrosourea).
- b. Anti-cancer agents not known to be myelosuppressive (e.g. not associated with reduced platelet or ANC counts): ≥ 7 days after the last dose of agent. See <https://www.cogmembers.org/site/disc/devtherapeutics/default.aspx> for commercial and Phase 1 investigational agent classifications. For agents not listed, the duration of this interval must be discussed with the study chair and the study-assigned Research Coordinator prior to enrollment.
- c. Antibodies: ≥ 21 days must have elapsed from infusion of last dose of antibody, and toxicity related to prior antibody therapy must be recovered to Grade ≤ 1 .
- d. Corticosteroids: See [Section 4.2.2.1](#). If used to modify immune adverse events related to prior therapy, ≥ 14 days must have elapsed since last dose of corticosteroid.

- e. Hematopoietic growth factors: ≥ 14 days after the last dose of a long-acting growth factor (e.g. pegfilgrastim) or 7 days for short-acting growth factor. For growth factors that have known adverse events occurring beyond 7 days after administration, this period must be extended beyond the time during which adverse events are known to occur. The duration of this interval must be discussed with the study chair and the study-assigned Research Coordinator.
- f. Interleukins, Interferons and Cytokines (other than hematopoietic growth factors): ≥ 21 days after the completion of interleukins, interferon or cytokines (other than hematopoietic growth factors)
- g. Stem cell Infusions (with or without TBI):
 - Allogeneic (non-autologous) bone marrow or stem cell transplant, or any stem cell infusion including DLI or boost infusion: ≥ 84 days after infusion and no evidence of GVHD.
 - Autologous stem cell infusion including boost infusion: ≥ 42 days.
- h. Cellular Therapy: ≥ 42 days after the completion of any type of cellular therapy (e.g. modified T cells, NK cells, dendritic cells, etc.)
- i. XRT/External Beam Irradiation including Protons: ≥ 14 days after local XRT; ≥ 150 days after TBI, craniospinal XRT or if radiation to $\geq 50\%$ of the pelvis; ≥ 42 days if other substantial BM radiation.

Note: Radiation may not be delivered to “measurable disease” tumor site(s) being used to follow response to subprotocol treatment.

- j. Radiopharmaceutical therapy (e.g., radiolabeled antibody, 131I-MIBG): ≥ 42 days after systemically administered radiopharmaceutical therapy.
- k. Patients must not have received prior exposure to BVD-523FB (ulixertinib) or other ERK inhibitors.

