5.1.1 Determination of Recommended Phase 2 Dose (RP2D)/Tolerable Dose

Dose Level	BVD-523FB (ulixertinib)Dose (mg/m ²)
-1	175 mg/m ² /dose PO BID* (300 mg BID Max Dose)
1*	260 mg/m²/dose PO BID* (450 mg BID Max Dose)
2	350 mg/m ² /dose PO BID* (600 mg BID Max Dose)

*Refer to the dosing nomogram in [Appendix V](#) for more information.

The starting BVD-523FB (ulixertinib) dose will be 260 mg/m²/dose (Dose Level 1), which is approximately 25% below the adult MTD. Accrual will be temporarily suspended after enrollment to the first 6 toxicity-evaluable subjects to assess for toxicity as outlined in [Section 11](#).

If there are fewer than 2 DLTs in the first 6 toxicity-evaluable subjects enrolled at the starting dose, the dose will be escalated to Dose Level 2. If ≥ 2 of the first 6 toxicity-evaluable subjects enrolled at Dose Level 2 have DLTs, all subsequent subjects will be enrolled at the original starting dose. Otherwise, remaining subjects will continue to enroll at Dose Level 2.

If there are 2 or more DLTs during cycle 1 among the first 6 toxicity-evaluable subjects enrolled at Dose Level 1, the next cohort will enroll at Dose Level -1. If ≥ 2 of the first 6 toxicity-evaluable subjects enrolled at the reduced dose have

DLTs, the study will be closed for toxicity. Otherwise, remaining subjects will continue to enroll at Dose Level -1.

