APPENDIX IV CORRELATIVE STUDIES

Correlative Study	Section.	Blood Volume		Tube Type
		Volume per Sample	Total Cycle 1	
Pharmacokinetics	8.4	2 mL	24 mL	K ₂ EDTA lavender top
Total Blood Volume in Cycle 1			24 mL	

Correlative Study	Section	Blood Volume		Tube Type
		Volume per Sample	Total Cycle 5 Day 1	
Circulating tumor DNA (optional)	8.5	
 For patients \geq 10 kg collect 20 mLs (10 mL per tube x 2 tubes) For patients \geq 5 kg but $<$ 10 kg collect 10 mL (one tube) For patients $<$ 5 kg research samples will not be collected 	10-20 mL	Streck Cell-Free DNA BCT tubes
Total Blood Volume in Cycle 5 Day 1			10-20 mL	

Correlative Study	Section	Blood Volume		Tube Type
		Volume per Sample	Total 'Time of progression' or 'End of protocol therapy'*	
Circulating tumor DNA (optional)	8.5	
 For patients \geq 10 kg collect 20 mLs (10 mL per tube x 2 tubes) For patients \geq 5 kg but $<$ 10 kg collect 10 mL (one tube) For patients $<$ 5 kg research samples will not be collected 	10-20 mL	Streck Cell-Free DNA BCT tubes
Total Blood Volume in 'Time of progression or End of protocol therapy'			10-20 mL	

*Only for patients receiving \geq 5 cycles of therapy only

APPENDIX V: BVD-523FB (ULIXERTINIB) DOSING NOMOGRAM**BVD-523FB (ulixertinib) Dose Assignment: 175 mg/m²/dose PO BID
(Dose Level -1)**

BSA (m ²)	BVD-523FB (ulixertinib) dosing	Total Daily dose (mg/day)	Total Daily pill count	Dose Reduction for Toxicity
0.54-0.72	Off-Study	Off-Study	Off-study	Off-study
0.73-1.07	150 mg PO BID	300	2	Off-Study
1.08-1.58	300 mg PO AM, 150 mg PO PM	450	3	150 mg PO BID
≥1.59	300 mg PO BID	600	4	300 mg PO AM, 150 mg PO PM

**BVD-523FB (ulixertinib) Dose Assignment: 260 mg/m²/dose PO BID
(Dose Level 1)**

BSA (m ²)	BVD-523FB (ulixertinib) dosing	Total Daily dose (mg/day)	Total Daily pill count	Dose Reduction for Toxicity
0.54-0.72	150 mg PO BID	300	2	off study
0.73-1.07	300 mg PO AM, 150 mg PO PM	450	3	150 mg PO BID
1.08-1.29	300 mg PO BID	600	4	300 mg PO AM, 150 mg PO PM
1.3-1.58	450 mg PO AM, 300 mg PO PM	750	5	300 mg PO AM, 150 mg PO PM
≥1.59	450 mg PO BID	900	6	300 mg PO BID

**BVD-523FB (ulixertinib) Dose Assignment: 350 mg/m²/dose PO BID
(Dose Level 2)**

BSA (m ²)	BVD-523FB (ulixertinib) dosing	Total Daily dose (mg/day)	Total Daily pill count	Dose Reduction for Toxicity
0.54-0.72	300 mg PO AM, 150 mg PO PM	450	3	150 mg PO BID
0.73-1.07	300 mg PO BID	600	4	300 mg PO AM, 150 mg PO PM

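### If the trial de-escalates to Dose Level -1, children with BSA 0.54-0.72 m² still meet eligibility but the nomogram has no dose for them

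*Combined protocol and SAP*

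**What the plan says.** - **Eligibility.** Section 4.1.3: "Patients must have a body surface area" of 0.54 m² or more at enrollment. No dose level is mentioned. Section 4.0 adds: "The eligibility criteria listed below are interpreted literally and cannot be waived".
- **De-escalation.** Section 5.1.1: "If there are 2 or more DLTs during cycle 1 among the first 6 toxicity-evaluable subjects enrolled at Dose Level 1", then "the next cohort will enroll at Dose Level -1". If fewer than two of the first six at that level have DLTs, "remaining subjects will continue to enroll at Dose Level -1". Neither step restricts BSA.
- **Assignment.** Section 3.8: "The dose level will be assigned via OPEN at the time of study enrollment". No BSA check is described there.
- **Nomogram.** The Appendix V table headed "Dose Assignment: 175 mg/m²/dose PO BID" (Dose Level -1) opens with the row "0.54-0.72 Off-Study Off-Study Off-study Off-study". The lowest BSA with a dose in that table is 0.73 m². The tables for Dose Levels 1 and 2 both give a dose for 0.54-0.72 m².
- **Disposition.** Section 10.1(j) removes from protocol therapy any enrolled patient who received no protocol treatment. Section 11.5 requires at least one dose for response evaluability and allows replacement of patients who are not evaluable. Section 11.1 allows for 15% inevaluable within the maximum of 49.

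**The concern.** The 0.54 m² floor fits what the nomogram can dose at Levels 1 and 2, but not at Level -1, where dosing starts at 0.73 m². Eligibility is settled before enrollment, the level is assigned at enrollment, and the nomogram is applied after that. If Level -1 is open, a site that follows the text in this order finds the conflict only once the child is on study.

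The child would by then have gone through consent, any required washout from earlier treatment, baseline imaging and the screening examinations, without being able to start. The trial would have spent one of its 49 places on a patient who contributes to neither the response nor the toxicity evaluation.

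**Working it through.** **1. Is the Off-Study row an error in the table?** Appendix V has 13 rows with a dose. In each, total daily dose divided by 150 mg (the only capsule strength in Section 9.1.3) equals the stated pill count. Delivered mg/m² per dose, taken as (daily dose / 2) / BSA at the band edges, is about 80% to 119% of nominal in those rows. For the 0.54-0.72 m² band at Level -1:

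- nominal dose: 175 × 0.54 = 94.5 mg to 175 × 0.72 = 126 mg, below one capsule;
- one capsule per dose: 150 / 0.54 = 278 to 150 / 0.72 = 208 mg/m², or 159% to 119% of 175.

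Section 5.1 does not allow capsules to be opened. The row therefore looks deliberate. What is missing is its counterpart in the eligibility and enrollment sections.

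**2. The passages side by side**

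| BSA 0.54-0.72 m² | Section 4.1.3 | Appendix V |
|---|---|---|
| Level 1 | admitted | 300 mg/day |
| Level 2 | admitted | 450 mg/day |
| Level -1 | admitted | Off-Study |

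**3. How likely is de-escalation?** Under the Section 5.1.1 rule, P(2 or more of 6) = 1 − (1−p)⁶ − 6p(1−p)⁵. The true DLT rate p is an assumption.

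- p = 10%: 1 − 0.531 − 0.354 = 11%
- p = 20%: 1 − 0.262 − 0.393 = 34%
- p = 30%: 1 − 0.118 − 0.303 = 58%

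**4. How likely is at least one affected child?** Suppose 20 − 6 = 14 primary-cohort enrollments follow at Level -1. With a share s of enrollees in the band, the chance of at least one is 1 − (1−s)¹⁴. The documents give no BSA distribution, so s is an assumption.

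| s | Given de-escalation | × 11% | × 34% | × 58% |
|---|---|---|---|---|
| 5% | 51% | 6% | 18% | 30% |
| 10% | 77% | 9% | 27% | 45% |
| 20% | 96% | 11% | 33% | 55% |

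The expected number, given de-escalation, is 14s = 0.7, 1.4 or 2.8.

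Fourteen is itself only a working figure. If two or more of the first six at Level -1 have DLTs, the study closes early. The rolling-six table in Section 11.2.2 can de-escalate after as few as two patients. If undosed children are replaced until 14 are dosed, the expected number becomes 14s/(1−s) = 0.74, 1.56 or 3.5.

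**5. Effect on sample size.** The plan's maximum reproduces: (20 + 21) / 0.85 = 48.2, rounded up to 49, which leaves 49 − 41 = 8 places for inevaluable patients at full size. The expected numbers above fit within that.

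**The case against.** The case for leaving the text alone has four parts.

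- **Appendix V already states a disposition.** It does, and the row looks intended. But Off-Study in a dosing table is not an eligibility rule, and it comes into play only after Section 4.1.3 has admitted the child and a level has been assigned.
- **There are checkpoints.** The Study Chair or Vice Chair should be notified before enrollment (3.6), an eligibility checklist is signed (3.5), and accrual pauses after the first six toxicity-evaluable patients (5.1.1). Any of these might catch a case. None, as described in the documents, carries a BSA limit. The checklist and the OPEN edit checks are not in the documents, so it cannot be said that OPEN lacks a check.
- **The problem may never arise.** This stands: if Level 1 does not de-escalate, every eligible BSA has a dose.
- **Few such children may enroll.** This also stands. Section 4.1.8 requires patients to swallow intact capsules, which may exclude many of the smallest. At assumed shares of 1% or 2%, the chance in step 4 is 13% or 25% given de-escalation, and about 5% or 8% after multiplying by the 34% trigger.

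A reader might infer that the gap biases the response rate. The documents do not support that: an undosed child is not evaluable under Section 11.5, enters neither numerator nor denominator, and may be replaced. A reader might also take 51%, 77% and 96% as the overall chance that a child is affected. They hold only given de-escalation and 14 enrollments at Level -1.

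**Conclusion.** The contradiction is certain on the text and needs no probability: Section 4.1.3 admits a BSA band that Appendix V does not dose at Level -1, and no other section closes the gap. Its occurrence is conditional on de-escalation from Level 1, with probability 11% to 58% over assumed DLT rates of 10% to 30%. The number of children affected cannot be computed. The chance of at least one is about 18% to 33% at a 20% DLT rate with assumed shares of 5% to 20%, and lower if fewer small children enroll.

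The consequence is a futile enrollment and a drawn-down allowance for inevaluable patients. The A'Hern decision rule is untouched. There is one related exposure: Section 5.1 recalculates the dose from BSA each cycle, so a patient on Level -1 whose BSA fell below 0.73 m² would reach the same row. The point should be settled because it concerns children enrolled without being treatable, and because settling it is cheap.

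**What to change.** Reconcile Sections 4.1.3, 3.8, 5.1.1 and Appendix V before any Dose Level -1 enrollment, so that the BSA range admitted at a dose level agrees with the range the nomogram doses there. The study committee decides which passage changes; no dose, BSA limit or clinical rule is proposed here. The same amendment should say what happens to a patient already on Level -1 whose recalculated BSA falls into the Off-Study row.

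The cost is one wording amendment, plus an update to the enrollment system if its checks, which are not in the documents, do not already match the agreed rule. Eligibility may become dependent on dose level, which sites would need to be told. The sample size and decision rule do not change.
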